11.1.7 Progression free survival

Progression free survival (per RECIST 1.1 as assessed by the ICR) will be defined as the time from the date of first dose until the date of objective disease progression or death (by any cause in the absence of progression) regardless of whether the patient withdraws from therapy or receives another anti-cancer therapy prior to progression. Patients who have not progressed or died at the time of analysis will be censored at the time of the latest date of assessment from their last evaluable RECIST 1.1 assessment. However, if the patient progresses or dies after 2 or more missed visits, the patient will be censored at the time of the latest evaluable RECIST 1.1 assessment. If the patient has no evaluable visits or does not have baseline data they will be censored at Day 1 unless they die within 2 visits of baseline.

The PFS time will always be derived based on scan/assessment dates not visit dates.

RECIST 1.1 assessments/scans contributing towards a particular visit may be performed on different dates. The following rules will be applied:

- Date of progression will be determined based on the earliest of the dates of the component that triggered the progression on the first set of scans that indicates progression.
- When censoring a patient for PFS the patient will be censored at the latest of the dates contributing to a particular overall visit assessment.

In the absence of clinically significant deterioration the investigational site is advised to continue the patient on MEDI4736 until progression has been confirmed.

For exploratory purposes, PFS will also be obtained using the irRECIST 1.1 data obtained from ICR. Objective disease progressions will require confirmation under this approach.

11.1.8 Overall survival

Overall survival is defined as the time from the date of first dose until death due to any cause. Any patient not known to have died at the time of analysis will be censored based on the last recorded date on which the patient was known to be alive.

Note: Survival calls will be made in the week following the date of data cut-off for the analysis, and if patients are confirmed to be alive or if the death date is after the data cut-off date these patients will be censored at the date of data cut-off. The status of ongoing, withdrawn (from the study) and “lost to follow-up” patients at the time of the final OS analysis should be obtained by the site personnel by checking the patient’s notes, hospital

records, contacting the patient's general practitioner and checking publicly-available death registries. In the event that the patient has actively withdrawn consent to the processing of their personal data, the vital status of the patient can be obtained by site personnel from publicly-available resources where it is possible to do so under applicable local laws.

11.1.9 Proportion of patients alive at 6 months and 12 months

The proportion of patients alive at 6 months and 12 months will be defined as the Kaplan-Meier estimate of OS at 6 months and 12 months.

11.1.10 Proportion of patients alive and progression free at 6 months and 12 months

The proportion of patients alive and progression free at 6 months (APF6) and alive and progression free at 12 months (APF12) will be respectively defined as the Kaplan-Meier estimate of PFS at 6 months and 12 months.

11.2 Calculation or derivation of safety variable(s)

11.2.1 Adverse events

Data from all cycles of treatment will be combined in the presentation of safety data. AEs (both in terms of MedDRA preferred terms and CTCAE grade) will be listed individually by patient.

Any AE occurring before treatment with MEDI4736 will be included in the data listings but will not be included in the summary tables of AEs.

Adverse events observed up until 90 days following discontinuation of MEDI4736 treatment or until the initiation of the first subsequent therapy following discontinuation of MEDI4736 treatment (whichever occurs first) will be used for reporting of all of the AE summary tables. This will more accurately depict AEs attributable to MEDI4736 only as a number of AEs up to 90 days following discontinuation of MEDI4736 are likely to be attributable to subsequent therapy. However, to assess the longer term toxicity profile, AE summaries will also be produced containing AEs observed up until 90 days following discontinuation of MEDI4736 treatment (ie without taking subsequent therapy into account). Any events in this period that occur after a patient has received further therapy for cancer (following discontinuation of MEDI4736) will be flagged in the data listings.

11.2.2 Other significant adverse events (OAEs)

During the evaluation of the AE data, an AstraZeneca/MedImmune medically qualified expert will review the list of AEs that were not reported as SAEs and AEs leading to discontinuation. Based on the expert's judgement, significant AEs of particular clinical importance may, after consultation with the Global Patient Safety Physician, be considered OAEs and reported as such in the CSR. A similar review of laboratory/vital signs/ECG data will be performed for identification of OAEs.

Examples of these are marked haematological and other laboratory abnormalities, and certain events that lead to intervention (other than those already classified as serious) or significant additional treatment.

11.2.3 Safety assessments

For production of outputs for vital signs, laboratory data, ECGs, and physical examination, the baseline value will be the latest result obtained prior to the start of investigational product.

Corrected calcium product will be derived during creation of the reporting database using the following formulas:

$$\text{Corrected Calcium (mmol/L)} = \text{Total Calcium (mmol/L)} + ([40 - \text{Albumin (G/L)}] \times 0.02)$$

The denominator used in laboratory summaries will only include evaluable patients, in other words those who had sufficient data to have the possibility of an abnormality.

For example:

- If a CTCAE criterion involves a change from baseline, evaluable patients would have both a pre-dose and at least 1 post-dose value recorded
- If a CTCAE criterion does not consider changes from baseline, to be evaluable the patient need only have 1 post dose-value recorded.

The denominator in vital signs data should include only those patients with recorded data.

11.3 Calculation or derivation of pharmacokinetic variables

11.3.1 PK non-compartmental analysis

The PK sample analyses will be performed at AstraZeneca/MedImmune R&D. The actual sampling times will be used in the PK calculations. MEDI4736 concentration data and summary statistics will be tabulated. Individual and mean blood MEDI4736 concentration-time profiles will be generated. Pharmacokinetic parameters will be determined using standard non-compartmental methods. The following PK parameters will be determined after the first and steady-state doses: peak and trough concentration (as data allow). Samples below the lower limit of quantification will be treated as missing in the analyses.

11.3.2 Population PK and exposure-response/safety analysis

A population PK model will be developed using a non-linear mixed-effects modelling approach in patients with NSCLC. The impact of physiologically-relevant patient characteristics (covariates) and disease on PK will be evaluated. The relationship between MEDI4736 PK exposure and the effect on safety and efficacy end points will be evaluated. The results of such an analysis will be reported in a separate report.

11.3.3 Immunogenicity analysis

Immunogenicity results will be analysed descriptively by summarizing the number and percentage of patients who develop detectable anti-MEDI4736 antibodies. The immunogenicity titre will be reported for samples confirmed positive for the presence of anti-MEDI4736 antibodies. The effect of immunogenicity on PK, pharmacodynamics, efficacy and safety will be evaluated.

11.4 Calculation or derivation of biomarker variable(s)

PD-L1 expression status (positive, negative) is defined as previously described (see Section 3.1).

11.5 Calculation or derivation of pharmacogenetic variables

In the case of genetic data, only the date the patient gave consent to participation in the genetic research and the date the blood sample was taken from the patient will be recorded in the eCRF and database. The genetic data generated from the study will be stored in the AstraZeneca LIMS database or other appropriate system. This database is a secure database, which is separate from the database used for the main study. Some or all of the dataset from the main study may be duplicated within the AstraZeneca LIMS database for exploratory genetic analysis. Data will be reported outside the CSR (please see [Appendix D](#)).

12. STATISTICAL METHODS AND SAMPLE SIZE DETERMINATION BY ASTRAZENECA

12.1 Description of analysis sets

A comprehensive SAP will be prepared with additional details to support analyses specified in the protocol. Table 9 gives a summary of outcome variables and analysis populations. The analysis of Cohort 2 requires some further considerations which are detailed further in Section 12.2.

Table 9 Summary of outcome variables and analysis populations

Outcome variable	Populations
Efficacy Data	
ORR	FAS (ITT)
DoR, DCR, TTR, PFS, and OS, proportion of patients alive at 6 and 12 months, APF6, APF12	FAS (ITT)
Demography	FAS (ITT)
World Health Organisation performance status	FAS (ITT)
PK data	PK
Safety Data	
Exposure	Safety
Adverse events	Safety
Laboratory measurements	Safety
Vital Signs	Safety

APF6 Alive and Progression Free at 6 months; APF12 Alive and Progression Free at 12 months; DCR Disease control rate; DoR Duration of response; FAS Full analysis set; ITT Intent-to-Treat; ORR Objective response rate; OS Overall survival; PFS Progression free survival; PK Pharmacokinetic; TTR Time to response.

12.1.1 Full analysis set (FAS)

Intention-to-treat: The statistical analysis of the efficacy of MEDI4736 will include all treated patients who have a baseline tumour assessment and have measurable disease at baseline according to the investigator site assessment. Patients who were enrolled but did not subsequently go on to receive investigational product are not included in the FAS population. This analysis set will be subsetted for the primary statistical analysis of the efficacy of MEDI4736 for ORR; namely all treated patients who have a baseline tumour assessment and have measurable disease at baseline according to the ICR.

12.1.2 Safety analysis set

All patients who received at least 1 dose of investigational product will be included in the safety population. When assessing safety and tolerability, summaries will be produced based on the safety analysis set.

12.1.3 PK analysis set

All patients who receive at least 1 dose of MEDI4736 per the protocol, for whom any post-dose data are available and do not violate or deviate from the protocol in ways that would significantly affect the PK analyses will be included in the PK analysis set.

12.2 Methods of statistical analyses

Generally, all analyses and reporting will be separated for each cohort. However, an exploratory analysis will be undertaken where Cohorts 1 and 2 are combined. Cohort 1 will include patients who are *EGFR/ALK* positive. Cohorts 2 and 3 will include patients with *EGFR/ALK* wild type status (ie, do not have *EGFR* TK mutations or *ALK* alterations or where *EGFR* TK mutation/*ALK* fusion status is unknown).

Exploratory testing of biological samples will be conducted after patients have entered this study, and this may include testing for *EGFR* mutation/*ALK* fusion status. If a patient entered the study with unknown *EGFR* TK mutation/*ALK* fusion status and is subsequently found to be *EGFR/ALK* positive, and during their treatment history they have received an EGFR or ALK TKI, they will be re-assigned to the *EGFR/ALK* positive cohort for the final data analysis. Patients with unknown status who are found to be *EGFR/ALK* positive but who have not received an EGFR or ALK TKI prior to entering the study will remain in the *EGFR/ALK* wild type cohort (see Section 3.2 for rationale). It is anticipated that the number of patients re-assigned to the *EGFR/ALK* positive cohort in this way will be very low. However, if there is a sufficient number of re-assignments that would compromise the number of patients available for the efficacy analysis in the *EGFR/ALK* wild type cohorts then further recruitment of patients to those cohorts may be necessary.

It is anticipated that Cohort 2 will be analysed first followed by Cohort 1 and then, finally, Cohort 3. In addition to presentation for each cohort, the safety data may be aggregated and presented overall at the time of the reporting of the second and third cohorts.

Subsequent to the availability of the PD-L1 diagnostic to determine PD-L1 positive patients at the $\geq 25\%$ cut-point, only those patients with a tumour that is determined to be PD-L1 positive from a central test are permitted into the study. In the case of those patients who were already recruited prior to the availability of this PD-L1 diagnostic, a PD-L1 status can be determined retrospectively based on the patient's pre-treatment tumour sample. The diagnostic itself has been based upon data external to this study (eg, from Study 1108) and the retrospective PD-L1 testing in this study has been completed only after the diagnostic, including the selected 25% threshold, was made available by [redacted]. Results generated to date have not retrospectively influenced this 25% cut-point selection. Similarly, the decision to use the $\geq 90\%$ cut-point in Cohort 3 was based upon data external to this study (Study 1108). For Cohorts 1 and 2, the analysis of PD-L1 positive patients will include all patients regardless of whether their PD-L1 status was determined prospectively or retrospectively.

For each cohort, the data cut-off for the analysis of ORR will take place approximately 24 weeks after the last patient is enrolled into each cohort.

The data cut-off for the final analysis of OS (secondary endpoint) will take place approximately 12 months after the last patient is enrolled into each cohort.

Descriptive statistics will be used for all variables, as appropriate. Continuous variables will be summarised by the number of observations, mean, standard deviation, median, minimum, and maximum. Categorical variables will be summarised by frequency counts and percentages for each category. Unless otherwise stated, percentages will be calculated out of the population total and for each cohort.

Baseline will be the last assessment of the variable under consideration prior to the intake of the first dose of investigational product, except for efficacy variables. For efficacy variables, baseline is defined as the last visit prior to enrolment.

Efficacy data will be summarised and analysed on the FAS (ie, it will follow the Intention to treat principle) and the FAS subset for measurable disease per ICR for the ORR primary analysis.

The primary analysis population of Cohorts 1 and 3 for the primary endpoint, ORR, and for the secondary endpoints is as follows:

- Cohort 1: PD-L1 positive patients ($\geq 25\%$ of tumour cells with membrane staining)
- Cohort 3: PD-L1 positive patients with $\geq 90\%$ of tumour cells with membrane staining

In Cohort 2, ORR in the PD-L1 positive group ($\geq 25\%$ of tumour cells with membrane staining) is the primary endpoint. Objective response rate in the non-squamous PD-L1 positive ($\geq 25\%$ of tumour cells with membrane staining) group, the $\geq 90\%$ PD-L1 positive group ($\geq 90\%$ of tumour cells with membrane staining), the $\geq 90\%$ PD-L1 positive group and the non-squamous $\geq 90\%$ PD-L1 positive group are key secondary endpoints.

For Cohort 2, the primary efficacy analysis of ORR will be upon the RECIST data based upon the ICR assessments. This will be primarily based upon all treated patients who have a baseline tumour assessment and have measurable disease at baseline according to the ICR. However, a sensitivity analysis will be performed upon all treated patients who have a baseline tumour assessment and have measurable disease at baseline according to the investigator (ie, the FAS). Other major efficacy endpoints using RECIST data based upon the ICR assessments will also have sensitivity analyses performed.

In Cohort 2, all the secondary efficacy endpoints will also be assessed for the non-squamous PD-L1 positive patients, the $\geq 90\%$ PD-L1 positive patients and the non-squamous $\geq 90\%$ PD-L1 positive patients. Furthermore, all efficacy will be assessed on PD-L1 negative patients, non-squamous PD-L1 negative patients, PD-L1 unselected patients, the $< 90\%$ PD-L1 patients ($< 90\%$ of tumour cells with membrane staining) and the non-squamous $< 90\%$ PD-L1 patients.

Safety presentations will show the PD-L1 positive patients, non-squamous PD-L1 positive patients, $\geq 90\%$ PD-L1 positive patients, non-squamous $\geq 90\%$ PD-L1 positive patients and all patients treated in Cohort 2.

Efficacy will also be investigated for a combined population of Cohorts 2 and 3 for PD-L1 positive patients with $\geq 90\%$ of tumour cells with membrane staining and also for non-squamous PD-L1 positive patients with $\geq 90\%$ of tumour cells with membrane staining.

In the subsequent efficacy and safety sections that follow, all analysis described as being 'by cohort' will use the above considerations with regards to the sub-populations to be presented.

A small number of exploratory outputs will investigate efficacy in the PD-L1 negative patients for Cohort 1 (should there be sufficient PD-L1 negative patients to warrant such an analysis), and additionally, for all patients in a combined population of Cohorts 1 and 2.

Safety data will be summarised based on the safety analysis set. No statistical hypothesis will be tested on efficacy and safety endpoints.

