
Other secondary objectives: To further assess the efficacy of MEDI4736 in terms of: DoR, DCR, TTR, PFS and OS in
 
 • PD-L1 positive patients ($\geq 25\%$ of tumour cells with membrane staining) • Non-squamous PD-L1 positive ($\geq 25\%$ of tumour cells with membrane staining) patients • PD-L1 positive patients with $\geq 90\%$ of tumour cells with membrane staining • Non-squamous PD-L1 positive patients with $\geq 90\%$ of tumour cells with membrane staining 
To assess the efficacy of MEDI4736 in
 
 • PD-L1 negative patients ($< 25\%$ of tumour cells with membrane staining) • Non-squamous PD-L1 negative ($< 25\%$ of tumour cells with membrane staining) patients • PD-L1 unselected patients (combined population of PD-L1 positive, PD-L1 negative and PD-L1 unknown patients who were enrolled under the original protocol [ie, prior to the amendment to only enrol PD-L1 positive patients]) • Patients with $< 90\%$ of tumour cells with PD-L1 membrane staining • Non-squamous patients with $< 90\%$ of tumour cells with PD-L1 membrane staining 	OS

Cohorts 2 and 3 To assess the efficacy of MEDI4736 in a combined population of Cohorts 2 and 3 for:
 
 • PD-L1 positive patients with $\geq 90\%$ of tumour cells with membrane staining • Non-squamous PD-L1 positive patients with $\geq 90\%$ of tumour cells with membrane staining 	ORR using Independent Central Review assessments according to RECIST 1.1 DoR using Independent Central Review assessments according to RECIST 1.1 DCR using Independent Central Review assessments according to RECIST 1.1 TTR using Independent Central Review assessments according to RECIST 1.1 PFS using Independent Central Review assessments according to RECIST 1.1 OS

All cohorts To assess the safety and tolerability profile of MEDI4736
	AEs, physical examinations, vital signs including blood pressure, pulse, electrocardiograms, and laboratory findings including clinical chemistry, haematology and urinalysis

All cohorts To assess the PK of MEDI4736
	Concentration of MEDI4736 in blood and non-compartmental PK parameters (such as peak concentration and trough, as data allow) (sparse sampling)

Secondary Objective:	Outcome Measure:

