12.2.1 Objective response rate

The primary endpoint, ORR, will be estimated for each cohort with 95% exact CIs. The primary analysis will be based on the programmatically derived ORR based on ICR assessments, and using all scans regardless of whether they were scheduled or not. An analysis of ORR using the results of the programmatically derived RECIST using the site investigator tumour data from all scans will be conducted as a sensitivity analysis to confirm the results of the primary analysis using data derived from the eCRFs. An additional sensitivity analysis will be performed on programmatically derived ORR using ICR data (RECIST modified for confirmation of progression) to determine if there is any difference when using progression confirmation rules. The primary analysis population for ORR will be a subset of the FAS population (ie, dosed patients with a baseline tumour assessment that indicates measurable disease per the ICR).

Summaries will be produced that present the number and percentage of patients with a tumour response (CR/PR). The number (%) of patients with a confirmed response and the number (%) of patients with a single visit response (ie, an unconfirmed response) will also be presented.

Summaries of ORR for each cohort will also be presented for the irRECIST 1.1 data obtained from the ICR.

A supportive analysis of patients with unselected PD-L1 status will be conducted consisting of a combined population of PD-L1 positive and PD-L1 negative/unknown patients, including those also enrolled after the protocol amendment to only recruit patients with PD-L1 positive status (ie, all Cohort 2 patients). This will use a weighted approach based on the observed

prevalence of PD-L1 positive, PD-L1 negative and PD-L1 unknown patients from the unselected sample pre-amendment. Further details of this approach will be provided in the SAP.

Furthermore, summaries of ORR (using the programmatically derived ORR based on ICR assessments) may also be presented by cohort for the PD-L1 negative patients in Cohort 1, and additionally, for all patients in a combined population of Cohorts 1 and 2.

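### Cohort 2's below-90% PD-L1 populations pool two enrolment periods with different entry rules, so their unweighted summaries depend on when the amendment took effect

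*Protocol*

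**What the plan says.** Protocol 2.2 makes "Patients with $< 90\%$ of tumour cells with PD-L1 membrane staining", and the non-squamous subset, secondary populations of Cohort 2. Section 12.2 repeats them in its list of groups for which all efficacy will be assessed: "PD-L1 unselected patients, the $< 90\%$ PD-L1 patients". Neither place limits these groups to an enrolment period or mentions weights or strata.

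Entry to Cohort 2 changed during the study. Section 12.2 says that, after the diagnostic became available, "only those patients with a tumour that is determined to be PD-L1 positive from a central test are permitted into the study". Patients treated earlier entered whatever their PD-L1 status and were classified retrospectively ("In the case of those patients who were already recruited prior to the availability of this PD-L1 diagnostic").

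The unselected population is handled differently. Section 2.2 restricts it to patients "who were enrolled under the original protocol [ie, prior to the amendment to only enrol PD-L1 positive patients". Section 12.2.1 adds a supportive response-rate analysis that uses everyone, "including those also enrolled after the protocol amendment to only recruit patients with PD-L1 positive status (ie, all Cohort 2 patients", weighted by the pre-amendment prevalence of positive, negative and unknown status.

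**The concern.** Patients with 25–89% staining could enter in both periods; patients below 25% could enter only in the first. A group defined as below 90% therefore has a mix set by how many all-comers were treated before the switch. Two otherwise identical studies with different amendment dates would report different below-90% response rates for the same drug effect.

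The pooled group answers neither question that a reader would bring to it: how patients between the two cut-points fare, or how an untested below-90% population fares. The protocol applies two safeguards against this mechanism to the unselected population and neither to the below-90% groups.

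**Working it through.** **Inputs**

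- Prevalence (synopsis, 3.1): 30% at ≥25% staining, 15% at ≥90%. The plan's own products reproduce: 700 × 0.30 = 210 and 700 × 0.15 = 105.
- Response rates (1.4, 3.2): 12/48 = 25% at ≥25%; 7/74 = 9.5% at <25% (stated as 10%); 7/18 = 38.9% at ≥90% (stated as about 39%).
- 94 PD-L1 positive patients in the cohort. The worked example in 12.3 counts retrospectively found positives towards the 94.
- Early all-comers in Cohort 2 (N0): not given. The example of 10 in 12.3 is hypothetical and concerns Cohort 1. I use 10 to 200.

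The plan gives no figure for the below-90% group.

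**Share of 25–89% tumours**

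Natural population: (0.30 − 0.15) / (1 − 0.15) = 0.15/0.85 = 17.6%.

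Pooled group: half of the 94 positives (0.15/0.30) lie at 25–89%, that is 47. Patients below 25% number 0.70 × N0. The share is 47 / (47 + 0.70 × N0).

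**Response rate in the 25–89% stratum, two assumptions**

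- A: the 18 patients lie within the 48, giving (12 − 7)/(48 − 18) = 5/30 = 16.7% (exact 95% CI 5.6% to 34.7%).
- B: 25% overall with a 50:50 split of positives, giving (0.25 − 0.5 × 0.389)/0.5 = 11.1%.

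**Response rate below 90%** = share × (rate at 25–89%) + (1 − share) × 7/74.

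Natural mix: A gives 10.7%, B gives 9.8%.

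| N0 | Patients <25% | Share 25–89% | ORR, A | Shift, A | ORR, B | Shift, B |
|---|---|---|---|---|---|---|
| 10 | 7 | 87% | 15.7% | 5.0 | 10.9% | 1.1 |
| 50 | 35 | 57% | 13.6% | 2.9 | 10.4% | 0.7 |
| 100 | 70 | 40% | 12.4% | 1.6 | 10.1% | 0.4 |
| 150 | 105 | 31% | 11.7% | 1.0 | 10.0% | 0.2 |
| 200 | 140 | 25% | 11.3% | 0.5 | 9.9% | 0.1 |

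Shifts are in percentage points and were taken before rounding; at N0 = 200 under A, for example, 11.27 − 10.73 = 0.54.

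The pooled mix would equal the natural one only with 47 × 0.70/0.15 = 219 patients below 25%, that is N0 = 219/0.70, or about 313.

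The synopsis and 3.1 can be read as 94 prospectively tested positives plus any found retrospectively. On that reading, N0 = 200 gives (94 + 60)/2 = 77 patients at 25–89%, a share of 77/217 = 35% and, under A, a rate of 12.0% (shift 1.3 points). The result for N0 = 10 hardly changes.

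**The case against.** The study is non-comparative, and 12.2 states that no hypothesis will be tested. A reader might infer that the below-90% group is the study's comparator for the 90% cut-point, and that pooling makes that cut-point look less useful. Under assumption A with 10 all-comers, the gap to 38.9% would indeed narrow from 28.2 to 23.2 points. But the protocol plans no comparison of ≥90% with <90%, and both cut-points were chosen on external data. That reading is not supported.

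A reader might also infer that progression-free survival, overall survival and duration of response are biased the same way. The document does not settle the direction. Section 1.1.2 cites lung-cancer data in which PD-L1 expression went with worse survival (20% against 49% beyond 3 years).

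On size, the largest shift needs very few all-comers. The below-25% group is an unconditional secondary group in Cohort 2, whereas in Cohort 1 it is conditional on sufficient numbers (2.3), which suggests that Cohort 2 has more than a handful. The 5/30 also subtracts data on file from a conference dataset that is not said to be the same. It implies 18/48 = 37.5% of positives at ≥90%, where the prevalences imply 50%. All of this stands and limits the size.

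For response rate, a reader can recover the 25–89% stratum by subtracting the ≥90% counts from the ≥25% counts. That also stands, but it does not work for Kaplan-Meier medians.

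Finally, the SAP is not among the documents and may add weights. However, 12.2 sets a default: percentages use the population total unless stated otherwise. Nothing else is stated for the below-90% groups, and 12.2.1 defers to the SAP only the details of the unselected weighting. As written, the protocol yields an unweighted pooled figure.

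**Conclusion.** The point holds as a flaw in how two secondary populations are defined. Their unweighted summaries depend on the timing of the amendment and describe no natural below-90% population.

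The change in mix is large: 87% to 25% of the group at 25–89% staining for 10 to 200 all-comers, against 18% naturally. The effect on response rate is modest and uncertain: about 5 down to 0.5 points upward under assumption A, and little over 1 point at most under B. These figures assume that the protocol's prevalences apply to Cohort 2 and that the external response rates carry over. The number of all-comers is unknown. No direction can be given for the time-to-event endpoints.

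The analyses are descriptive. The primary endpoint, the key secondary groups and Cohort 3 are untouched.

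**What to change.** In 12.2 and 12.2.1, report Cohort 2 efficacy for 25–89% and below-25% as separate strata, overall and in non-squamous patients. Form any below-90% estimate in one of two ways:

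- from patients enrolled under the original protocol only, as 2.2 already does for unselected patients; or
- by weighting the two strata with their pre-amendment prevalences.

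The weights must be newly derived from the retrospective PD-L1 testing. Those in 12.2.1 cover positive, negative and unknown status and do not split the positives at 90%, so they cannot be reused.

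The cost is a little programming and a wider interval for the below-90% estimate. No new data collection is needed beyond the retrospective testing.
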